7. PLANNED ANALYSIS

The format of the listings and tables will follow the BI standards "Standards for reporting of clinical trials and project summaries" (6), with the exception of those generated for PK calculations following BI standards for PK/PD analysis (7,8).

The individual values of all patients will be listed, sorted by use of SGLT2i (Yes/No), type of diabetes mellitus (type 1/type 2), dose group of study treatment (placebo/BI 685509), patient number, and visit (if visit is applicable in the respective listing). AE listings will be sorted by study treatment (see Section 7.8.1 below for details). The listings will be contained in Appendix 16.2 of the CTR.

For end-of-text tables, the set of summary statistics of continuous variables (for non-PK parameters) is:

N	number of non-missing observations
Mean	arithmetic mean
SD	standard deviation
SE	standard error
Min	minimum
Median	median
Max	maximum

For plasma concentrations, as well as for PK parameters, the following descriptive statistics will additionally be calculated:

CV	arithmetic coefficient of variation
gMean	geometric mean
gCV	geometric coefficient of variation
P10	10 th percentile
Q1	1 st quartile
Q3	3 rd quartile
P90	90 th percentile

The data format for descriptive statistics of plasma concentrations will be identical with the data format of the respective concentrations. The descriptive statistics of PK parameters will be calculated using the individual values with the number of decimal places as provided by the evaluation program. Then the individual values as well as the descriptive statistics will be reported with three significant digits in the CTR.

Tabulations of frequencies for categorical data will include all possible categories and will display the number of observations in a category as well as the percentage (%). Percentages will be rounded to one decimal place. The category missing will be displayed if and only if there actually are missing values. Percentages will be based on all patients in the respective patient set whether they have non-missing values or not.

Units of variables should be given in the titles or column/row descriptors in square brackets (e.g. [mg]).

7.1 DEMOGRAPHIC AND OTHER BASELINE CHARACTERISTICS

Only descriptive statistics are planned for this section of the report. The data will be summarised by dose group of study treatment, and in total.

7.2 CONCOMITANT DISEASES AND MEDICATION

Only descriptive statistics are planned for this section of the CTR, based on the RS.

Concomitant diseases and concomitant non-drug therapies will be coded according to the most recent version of the Medical Dictionary for Regulatory Activities (MedDRA). Concomitant medication will be coded according to the most recent version of the World Health Organisation – Drug Dictionary. The coding version number will be displayed as a footnote in the respective output.

The frequency [N (%)] of patients with different concomitant diseases (baseline conditions) will be presented.

A medication/non-drug therapy will be considered concomitant to treatment if it

- Is ongoing at the start of randomised trial treatment or
- Starts within the on-treatment period (see [Section 6.1](#) for a definition of study analysis phases).

A medication/non-drug therapy will be considered as prior medication/non-drug therapy, if the end date of the medication/therapy is at any time prior to the start of the randomised trial treatment.

Concomitant medication use will be summarised with frequency and percentage of patients by ATC3 class and preferred name. Summaries will be presented for concomitant medication starting any time prior to start of trial treatment and starting any time during the on-treatment period (cf. [Section 6.1](#)).

Concomitant use of non-drug therapies will be summarised with frequency and percentage. Summaries will be presented for concomitant non-drug therapies starting any time prior to start of trial treatment and starting any time during the on-treatment period (cf. [Section 6.1](#)).

Restrictions regarding concomitant treatment during the study periods are defined in Section 4.2.2.1 of the CTP.

The relevance of the concomitant therapies to the evaluation of PK will be decided no later than at the RPM.

7.3 TREATMENT COMPLIANCE

Only descriptive statistics are planned according to percentage of patients meeting the compliance. Descriptive statistics will be provided overall (see [Section 5.4.2](#)).

7.4 PRIMARY ENDPOINT(S)

7.4.1 Primary analysis of the primary endpoint(s)

The primary endpoint will be analysed in combination with the primary approach of handling ICEs (see [Section 5.1](#)). The FAS is the main analysis set for the analysis of efficacy: the patient set includes all patients who had at least one baseline measurement of 10 hour UACR in week -2, -1, or 0 and at least one post-baseline measurement after week 6.

Refer to Section 7.2.2 of the CTP for a description of the statistical analysis for the change from baseline in log transformed UACR measured in 10-hour urine at 20 weeks of trial treatment.

The adjusted mean reduction in log transformed UACR in 10-hour urine from baseline at 20 weeks and its standard deviation will be obtained from MMRM for the placebo and treatment groups. For the MMRM model, derived UACRs at baseline, visit 6, visit 7, and EoT, which were described in [Section 6.6.2.1](#), will be used.

SAS code for **the MMRM model** will be based on the following structure:

```
PROC MIXED DATA=alldat cl method=reml;

CLASS visit trt subject;

MODEL chg = base*visit visit*trt typediabetes SGLT2ibase / ddfm=kr s CL;
REPEATED visit / subject= subject type=un r rcorr;

LSMEANS visit*trt / pdiff=all om cl alpha=0.05 slice=visit;

RUN;
```

In the event of model non-convergence, the methods described in [Section 10.1](#) will be attempted (in order) to overcome it.

Multiple Comparisons Procedure - Modelling (MCP-Mod) Analysis

For the primary analysis, the dose-response relationship will be modelled using the total daily doses: 3 mg, 6 mg, and 9 mg. The multiple comparison procedure will then be implemented using optimal contrast tests which control the family-wise type I error rate at a one-sided $\alpha = 0.05$. For the MCPMod test, the optimal contrasts of each candidate model are calculated using the R-function optCont.

For the final evaluation, the contrast will be provided using the expected model means from the candidate set and the estimated variance-covariance matrix extracted from the MMRM model.

Once the significance of a dose-response signal is established, the dose-response profile and the target dose can be estimated using a model averaging approach for significant models.

To select a dose estimation model out of the set of significant models, estimates for each dose group will be calculated and will be based on the final dose-response model. The choice of the target dose will be based upon efficacy as well as considering safety and other relevant information.

The following displays are planned:

- Table of the updated contrast coefficients per dose group and candidate model, together with the MCPMod test statistics and p-values for each model and the critical value
- For averaging model, figure of the dose-response curve
- For all significant model shapes, figures of the dose-response curve plus 90% and 95% confidence bands (of the predicated shape) and 90% and 95% CIs per dose (estimated from MMRM)
- For all significant model shapes, figure with the placebo corrected dose-response curve plus 95% confidence band (of the predicated shape).

Estimates for each dose group will be calculated and will be based on the final dose-response model. R code to perform the evaluations is available in [Section 10.2](#).

7.5 SECONDARY ENDPOINT(S)

7.5.1 Key secondary endpoint(s)

This section is not applicable as no key secondary endpoint has been specified in the protocol.

7.5.2 (Other) Secondary endpoint(s)

The analysis of the change of UACR in FMV urine after 20 weeks of trial treatment will be performed by using the same MMRM/MCPMod as for the primary analysis.

For the secondary endpoints,

- Proportion of patients achieving UACR decreases in 10-hour urine of at least 20% from baseline after 20 weeks of trial treatment
- Proportion of patients achieving UACR decreases in FMV urine of at least 20% from baseline after 20 weeks of trial treatment

the following analyses will be implemented:

- A logistic regression with Last Observation Carried Forward (LOCF)
- A logistic regression excluding patients with missing UACR at baseline/EoT
- A two sample proportion test with LOCF
- A two sample proportion test excluding patients with missing UACR at baseline/EoT

Treatment, SGLT2i use at baseline, and type of diabetes will be used as covariates in the logistic regression model.

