7.2.2 Primary endpoint analyses

The primary objectives are to demonstrate a non-flat dose response curve, evaluate the quantitative treatment effect size, and evaluate the dose-response relationship. The primary analysis will be performed on the FAS.

For the proof of concept (PoC) and dose finding, both multiple comparison procedures and modelling techniques (MCPMod) will be applied. The primary estimand of interest is the treatment effect using a primary approach. In the primary approach, trial medication is assumed to be taken as randomised and an intercurrent event is defined as an event of treatment discontinuation, death, or dropin/dropout of SGLT2i. The primary approach for primary analysis will include all data prior to intercurrent event. Any data collected after the intercurrent event will not be included in the primary analysis. The resulting missing data will be assumed to be missing at random (MAR).

The three different approaches for handling ICEs are summarized in the [Table 7.2.2: 1](#) below.

Table 7.2.2: 1 Summary of strategies for handling ICEs

Estimand strategy name	Treatment	ICE handling
Primary approach	Randomised treatment	Study med d/c: include data prior to study med d/c. Death: include data prior to death. SGLT2i initiation/discontinuation: include data prior to SGLT2i start/stop.

Table 7.2.2: 1 Summary of strategies for handling ICEs cont.

Estimand strategy name	Treatment	ICE handling
[REDACTED]	[REDACTED]	[REDACTED]
[REDACTED]	[REDACTED]	[REDACTED]

Treatment effect

The primary analysis will first address a dose relationship between doses of BI 685509 and placebo. The analysis will include the fixed, categorical effect of treatment at each visit, and the fixed continuous effects of baseline log transformed UACR at each visit. Visit will be treated as the repeated measure with an unstructured covariance structure used to model the within-patient measurements.

To conduct multiple comparison in MCPMod across doses, covariate adjusted fixed effect estimates of average response for each dose group and the covariance matrix will be extracted from the fit by the following MMRM and used for MCPMod analysis.

Statistical model (MMRM):

$$y_{ijklm} = \beta_j U_i + \tau_{jk} + \eta_l + \psi_m + e_{ij},$$

where

$$e_{ij} \sim N(0, \Sigma),$$

y_{ijkm} = reduction in log transformed UACR at visit j from baseline for subject i in stratum m ($m=1,2$) receiving treatment k ($k=1,\dots,4$),

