5. ENDPOINTS

5.1 PRIMARY ENDPOINT(S)

Please refer to the protocol.

The three different approaches for handling intercurrent events (ICEs) are summarised in the table below:

Estimand strategy name	Treatment	ICE handling
Primary approach	Randomised treatment	Study med d/c: include data prior to study med d/c. Death: include data prior to death. SGLT2i initiation/discontinuation: include data prior to SGLT2i start/stop.
Supplementary 1	Randomised treatment	Study med d/c: include all available data. Death: include data prior to death. SGLT2i initiation/discontinuation: include all available data.
Supplementary 2	Actual final treatment	Study med d/c: include data prior to study med d/c. Death: include data prior to death. SGLT2i initiation/discontinuation: include data prior to SGLT2i start/stop.

SGLT2i = Sodium-Glucose co-Transporter-2 Inhibitor

Note that the table above should be used along with [Table 6.6.2.1:1](#) to derive endpoints for primary, supplementary 1, and supplementary 2 analysis.

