6.6.2 Efficacy data

6.6.2.1 Primary endpoint

Missing data for primary analysis will not be imputed:

- If some UACR value(s) for UACR at baseline is (/are) missing, all available UACR samples in week -2, -1, and 0 will be used to derive UACR at baseline.
- If any UACR value after randomisation is missing, the missing UACR will not be imputed; missing UACR due to ICEs will not be imputed.

The Mixed-effect Model for Repeated Measures (MMRM) approach used for the primary analysis (see [Section 7.4.1](#)) allows for missing data, assuming the missing data mechanism is ignorable. Even patients with only one post-baseline assessment can be included in the model and can, therefore, participate in variance estimation. The statistical model assumes that patients who had an ICE would have behaved similarly to those who remained in the study. The table below describes how/when to derive UACR values for MMRM:

Table 6.6.2.1: 1 Principal rule of UACR derivation for MMRM

UACRs for MMRM	UACR at baseline	UACR at visit 6	UACR at visit 7	UACR at EoT
Visits need to be included	First Morning Void (FMV) or 10-hour urine UACR baseline is defined as the mean of all non-missing assessments from Visit 2 until prior to the first intake of trial medication.	All available scheduled visits at visit 6	All available scheduled visits at visit 7	All available scheduled visits between visit 8 and EoT
Derivation	Average of all available UACR measurements defined at each visit			

Note: all available/scheduled UACR measurements will be used: no imputation for missing UACR measurement; this rule will be applied to FMV and 10-hour urine samples, respectively.

Sensitivity analyses will be conducted to investigate the potential effect of ICE handling approaches on the results of the primary analysis. Details about implementation of the sensitivity statistical analyses are described in [Section 7.4](#).

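### The logistic model for the 20% responder endpoints (SAP 7.5.2) omits baseline log UACR, which the MMRM includes; adding it is cheap and may gain a little precision

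*SAP*

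**What the plan says.** For each responder endpoint SAP 7.5.2 lists four analyses: logistic regression and a two-sample comparison of proportions, each under two rules for missing values. The logistic versions are "A logistic regression with Last Observation Carried Forward (LOCF") and "A logistic regression excluding patients with missing UACR at baseline/EoT". None of the four is named as the main one. The covariates are given in one sentence: "Treatment, SGLT2i use at baseline, and type of diabetes will be used as covariates in the logistic regression model".

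The continuous endpoints are treated differently. Protocol 7.2.2 puts into the MMRM "the fixed continuous effects of baseline log transformed UACR at each visit", and the code in SAP 7.4.1 reads "MODEL chg = base*visit visit*trt typediabetes SGLT2ibase / ddfm=kr s CL". SAP 7.5.2 uses that same model for the change in first morning void UACR. Among the secondary UACR models, only the responder model drops baseline.

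On missing values, SAP 6.6.2.2 applies the derivation table of SAP 6.6.2.1 to baseline and EoT. The EoT value averages "All available scheduled visits between visit 8 and EoT", so it is missing only if no usable sample exists in that whole period. SAP 6.6.2.2 also mentions imputation as a possibility, without a method, and refers to Section 7. Protocol 7.2.3 plans the response rate descriptively. SAP 5.2.1 states that there is no key secondary endpoint.

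**The concern.** Response is a cut of the log change from baseline at ln 0.8. If baseline predicts change, it predicts response, and a model without it leaves explainable variation in the comparison. Some dependence is plausible through regression to the mean, though averaging the baseline over up to six sampling days (two each at weeks -2, -1 and 0) dampens it. The plan already judges baseline worth including for the change on which response is based, and gives no reason for leaving it out here.

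At stake is some power and precision for two secondary endpoints, together with clarity about which of four results per endpoint is the one to read.

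**Working it through.** **Inputs from the documents.** 60 patients per active dose and 60 pooled placebo (Protocol 7.4); assumed effects 0, 0.10, 0.20, 0.35 on the log scale and 88.5% power at one-sided 5% (Protocol 7.5); about 10% type 1 diabetes (Protocol 3.1); response threshold 20%.

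**Assumed, because not stated.** SD of the log change, correlation of baseline with change, 50% SGLT2i use, no mean change on placebo. SAP 7.5.2 sets no significance level and names no dose comparison, so 9 mg against placebo is used, at one-sided 5% as for the primary endpoint and also at two-sided 5%.

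**Step 1: the plan's own figure.** The 88.5% cannot be reproduced directly without an SD. With the five candidate shapes of Protocol 7.5, optimal contrasts and 60 per group, MCPMod power is 91.0% at SD 0.65 and 86.9% at SD 0.70. Solving for 88.5% gives SD of about 0.68.

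**Step 2: responder rates.** Response means log change at or below ln 0.8 = -0.223.
- Placebo: Phi(-0.223/0.68) = Phi(-0.328) = 37.1%.
- 9 mg: Phi((-0.223 + 0.35)/0.68) = Phi(0.187) = 57.4%.

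**Step 3: power without baseline.** The difference is 0.574 - 0.371 = 0.203. The null SE is sqrt(2 x 0.4725 x 0.5275/60) = 0.0912. The SE under the alternative is sqrt((0.371 x 0.629 + 0.574 x 0.426)/60) = 0.0892. Power = Phi((0.203 - 1.645 x 0.0912)/0.0892), about 72% one-sided.

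**Step 4: add baseline.** Logistic Wald test with treatment, SGLT2i use and diabetes type, without and with baseline log UACR; complete data; 20,000 simulated trials per case (Monte Carlo SE about 0.3 points).

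| Assumed correlation | One-sided 5%: without / with | Gain | Two-sided 5%: without / with | Gain |
|---|---|---|---|---|
| 0 | 72.2 / 72.1% | -0.1 | 60.7 / 60.4% | -0.3 |
| -0.2 | 72.4 / 73.2% | +0.8 | 60.8 / 61.7% | +0.9 |
| -0.3 | 71.9 / 74.1% | +2.2 | 60.6 / 62.7% | +2.1 |
| -0.4 | 72.5 / 76.1% | +3.6 | 60.7 / 65.0% | +4.3 |

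A second simulation at the same SD gave one-sided 72.6 / 72.7, 72.2 / 72.8, 71.8 / 74.0 and 72.5 / 76.6% for the same four correlations. Type I error at one-sided 5% was 5.0 to 5.2% with or without baseline.

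**Step 5: other responder rates.** With 20% on placebo (37% active) the gain at 0, -0.3 and -0.4 is 0, +1.9 and +3.0 points. With 7.1% (17% active) it is 0, +1.5 and +2.8. If rates resembled the earlier patient trial in Protocol 1.2 (7.1% placebo in morning void, 50% active in 10-hour urine), power is about 99% either way and there is no gain.

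**Step 6: missing EoT values, illustration only.** The documents give no stopping rates. Suppose 25% of active Visit 7 non-responders stop and 5% of everyone else. With baseline in the model, visit correlation 0.6 and baseline correlation -0.3, the risk difference is off by +2.3 points (complete case), -2.9 (LOCF) and 0.0 (multiple imputation under MAR). Type I error is 7.7, 2.5 and 4.3%. If stopping is unrelated to outcome (15% active, 5% placebo), no method is biased and power is 71.0, 74.9 and 72.5%. With the 25% / 5% pattern in both arms, bias stays within 0.2 points and power is 67.6, 74.3 and 70.4%. In these last two cases LOCF beats imputation by 74.9 - 72.5 = 2.4 and 74.3 - 70.4 = 3.9 points (Monte Carlo SE about 0.6 points, 6,000 trials).

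**The case against.** The strongest defence is that the planned model is valid. It adjusts for both stratification factors, response is already relative to the patient's own baseline, and type I error is correct. The gain rests on an unstated correlation and vanishes when that is near zero. Adding baseline also makes the odds ratio conditional on it. Protocol 1.2 reports no 10-hour placebo responders in the earlier patient trial; at 7.1%, 60 placebo patients would yield about 0.071 x 60 = 4.3, so separation is a real possibility. All of this stands, and it keeps the point small. Separation with zero placebo responders would affect the planned model too.

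Three stronger readings are tempting and not supported.

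- *The SAP has no handling of missing responder data under MAR.* Protocol 7.2.2 does say of the primary analysis "The resulting missing data will be assumed to be missing at random (MAR"), and 7.5.2 specifies only LOCF and exclusion. But SAP 6.6.2.2 leaves imputation open, and some SAP sections, including Section 10, are not in the available text. Complete-case logistic regression is also valid when missingness depends only on the model's covariates.
- *LOCF and complete case are biased here, so multiple imputation must be the main method.* The bias in Step 6 needs stopping that depends on interim UACR and differs by arm. The discontinuation criteria in Protocol 3.3.4.1 contain no UACR or lack-of-efficacy rule. Elsewhere imputation loses power to LOCF.
- *Four unranked analyses inflate the trial's error rate.* No alpha is assigned to these endpoints. The chance that at least one of the four is positive under the null at one-sided 5% was 5.6% with almost no dropout and 9.8% with unequal dropout settings (SD 0.65). That bears on selective reading of the results, not on the trial's conclusion.

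**Conclusion.** The point holds as a modest gain in precision, not as an error. The responder model omits a covariate that is already collected and already used for the continuous endpoints. Including it changes one-sided power by about 0 to +4 points for correlations of 0 to -0.4, at SD 0.68, 60 per arm, complete data and about 37% against 57% responders. It leaves type I error at about 5% and gains nothing where power is near 99%. Naming a main analysis is a matter of missing detail. The missing-data observation is an optional secondary note: LOCF and complete case can err in opposite directions, but only under stopping patterns that the documents neither state nor imply. Overall impact is minor.

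**What to change.** In SAP 7.5.2:

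1. Add baseline log UACR of the matching urine type (10-hour or first morning void) to the logistic covariates.
2. Label that adjusted logistic regression as the main responder analysis and the two-sample tests as supportive. State which of the two existing missing-value rules goes with it; the other remains a labelled sensitivity analysis.
3. Say that the odds ratio is conditional on baseline, and name a separation-robust fit such as Firth's in case placebo responders are sparse.

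Optionally, replace the open remark on imputation in SAP 6.6.2.2 by a defined sensitivity analysis: impute missing EoT log UACR under the primary MAR assumption and its intercurrent-event rule ("Study med d/c: include data prior to study med d/c"), then derive response. Making this the main method would be a trade-off: it removes bias under differential stopping, targets on-treatment response, and costs 2 to 4 points of power against LOCF in the other two cases of Step 6.

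The cost is SAP wording and modest programming before treatment information is released; no new data are needed.

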7.7 EXTENT OF EXPOSURE

Descriptive statistics are planned for this section of the CTR based on the TS. The date and time of each drug administration will be listed for each patient.

7.8 SAFETY ANALYSIS

All safety analyses will be performed on the TS following BI standards. No hypothesis testing is planned. All safety analyses will be performed on treatment set.

7.8.1 Adverse Events

Analyses of AEs will be descriptive in nature. All analyses of AEs will be based on the number of patients with AEs and NOT on the number of AEs.

Furthermore, for analysis of AE attributes such as duration, severity, etc. multiple AE occurrence data on the CRF, will be collapsed into AE episodes provided that all of the following applies:

- The same MedDRA lowest level term was reported for the occurrences
- The occurrences were time-overlapping or time-adjacent (time-adjacency of 2 occurrences is given if the second occurrence started on the same day or on the day after the end of the first occurrence)
- Treatment did not change between the onset of the occurrences OR treatment changed between the onset of the occurrences, but no deterioration was observed for the later occurrence

For further details on summarisation of AE data, please refer to "Analysis and presentation of adverse event data from Clinical Trials" [\(9\)](#) and "Handling of missing and incomplete AE da [\(4\)](#).

The analysis of AEs will be based on the concept of TEAEs. That means that all AEs occurring between first drug intake until 7 days after last drug intake will be assigned to the randomised treatment. All AEs occurring before first drug intake will be assigned to 'screening' and all AEs occurring after last drug intake + 7 days will be assigned to 'follow-up' (for listings only). AEs that start before first drug intake and deteriorate under treatment will also be considered as 'treatment-emergent'. For details on the treatment definition, see [Section 6.1](#).

If only the start date of an AE is collected (without start time), any AE occurrence on the same day as the first BI 685509 administration will be assigned to the on-treatment phase. AEs will also be summarised by the treatment at the onset of AE for any drug-related AE. In addition, a summary of patients with down-titration due to AE will be provided.

An overall summary of AEs will be presented.

Frequencies [N (%)] of patients with AEs will be summarised by dose group, primary system organ class, preferred term (using MedDRA), and intensity. Separate tables will be provided for patients with serious AEs (SAEs), patients with AEs of Special Interest (AESIs), patients with fatal AEs, and patients with discontinuations due to AEs.

Regarding AESIs, summaries of AESIs of hypotension and syncope will be presented for both patient-based and event-based analyses. An individual episode of hypotension will be considered as significant or non-significant based on baseline BP and the lowest BP during the episode. Criteria for significant hypotensive episode are:

- For patients with baseline SBP ≤ 140 : decrease $((\text{lowest SBP during the episode} - \text{baseline SBP}) / (\text{baseline SBP})) \geq 30\%$
- For patients with baseline SBP > 140 : decrease $((\text{lowest SBP during the episode} - \text{baseline SBP}) / (\text{baseline SBP})) \geq 40\%$
- Or, lowest SBP during the episode < 90
- For patients with baseline DBP ≤ 70 : $((\text{lowest DBP during the episode} - \text{baseline DBP}) / (\text{baseline DBP})) \geq 30\%$
- For patients with baseline DBP > 70 : $((\text{lowest DBP during the episode} - \text{baseline DBP}) / (\text{baseline SBP})) \geq 40\%$
- Or, lowest DBP during the episode < 50
- Lowest mean arterial pressure (MAP) during the episode < 70

Details of the AESI of Hypotension and Syncope will be also listed.

Category	Safety topic	Definition
AESI	Hypotension	Investigator-reported, as a dedicated AE category on the AE eCRF page
AESI	Syncope	Investigator-reported, as a dedicated AE category on the AE eCRF page

In addition, potential DILI, acute kidney injury, and QT-interval prolongation are defined as follows:

- Potential DILI, defined as: Narrow sub-SMQ ‘Liver related investigations, signs and symptoms’, narrow sub-SMQ ‘Cholestasis and jaundice of hepatic origin’, narrow sub-SMQ ‘Hepatitis, non-infectious’ and narrow sub-SMQ ‘Hepatic failure, fibrosis and cirrhosis and other liver damage-related conditions’, or investigator-reported AESIs.
- Acute kidney injury, defined as: SMQ ‘Acute renal failure’, narrow scope
- QT-interval prolongation, defined as: SMQ ‘Torsade de points/QT prolongation’, narrow scope excluding the PT ‘Syncope’.

Summaries of potential DILI, acute kidney injury, and QT-interval prolongation will be presented for patient-based analyses.

